### 9.2.6. Respiratory Tract Assessment Grading: Erythema and Induration

Erythema and Induration of the nasal cavity will be graded as follows:

Parameter	Grade 1	Grade 2	Grade 3
Erythema (Redness)	Very slight or barely perceptible redness	Well defined redness	Moderate to severe beet redness to eschar

Parameter	Grade 1	Grade 2	Grade 3
Induration (Swelling or edema)	Very slight or barely perceptible swelling	Slight swelling (edges of area well-defined by definite raising)	Moderate swelling (edges raised approximately 1 mm)

**9.2.7. Procedures to be Followed in the Event of Abnormal Laboratory Test Values or Abnormal Clinical Findings**

The site principal investigator or appropriate sub-investigator is responsible for recording all AE/SAEs that are observed or reported during this trial, regardless of the relationship to study product. AE/SAEs, abnormal laboratory test values, or abnormal clinical findings will be collected, assessed, documented, reported, and followed appropriately.

### **9.3. Reporting Procedures**

Solicited upper respiratory assessment, respiratory tract assessment, and systemic reactogenicity events will be documented and reported from the time of experimental (first) study vaccination through 7 days after vaccination.

Unsolicited non-serious AEs will be documented and reported from the time of the first study vaccination through approximately 21 days after the first study vaccination.

SAEs will be documented and reported from the time of the first study vaccination through 12 months after the first vaccination.

AESIs (wheezing and otitis media) and NOCMCs will be documented and reported from the time of first study vaccination through approximately 3 months after first study vaccination.

#### **9.3.1 Serious Adverse Events**

SAEs will be followed until resolution even if this extends beyond the study-reporting period. Resolution of an AE is defined as the return to pretreatment status or stabilization of the condition with the expectation that it will remain chronic.

**Any AE that meets a protocol-defined serious criterion must be submitted immediately (within 24 hours of site awareness) on an SAE form to the DMID Pharmacovigilance Group at the following address:**

**DMID Pharmacovigilance Group  
Clinical Research Operations and Management Support (CROMS)  
[name]  
[name]  
SAE Hot Line: [name] (US) or [name] (outside US)  
SAE [contact] (US) or [name] (outside US)  
SAE Email Address: [[contact]](mailto:[contact])**

In addition to the SAE form, selected SAE data fields must also be entered into AdvantageEDCSM. Please see the protocol-specific MOP for details regarding this procedure.

Other supporting documentation of the event may be requested by the DMID Pharmacovigilance Group and should be provided as soon as possible.

The site will send a copy of the SAE report(s) to the ISM (as deemed necessary) when they are provided to the DMID Pharmacovigilance Group. The DMID Medical Monitor and DMID

Clinical Project Manager will be notified of the SAE by the DMID Pharmacovigilance Group. The DMID Medical Monitor will review and assess the SAE for regulatory reporting and potential impact on study subject safety and protocol conduct.

At any time after completion of this trial, if the site principal investigator or appropriate sub-investigator becomes aware of an SAE that is suspected to be related to study product, the site principal investigator or appropriate sub-investigator will report the event to the DMID Pharmacovigilance Group.

### **9.3.2. Regulatory Reporting for Studies Conducted Under DMID-Sponsored IND**

Following notification from the site principal investigator or appropriate sub-investigator, DMID, the Investigational New Drug (IND) sponsor, will report any suspected adverse reaction that is both serious and unexpected. DMID will report an AE as a suspected adverse reaction only if there is evidence to suggest a causal relationship between the drug and the AE. DMID will notify FDA and all participating site principal investigators (i.e., all principal investigators to whom the sponsor is providing drug under its IND(s) or under any principal investigator's IND(s)) in an IND safety report of potential serious risks from clinical trials or any other source, as soon as possible, but in no case later than 15 calendar days after the sponsor determines that the information qualifies for reporting as specified in 21 CFR Part 312.32. DMID will also notify FDA of any unexpected fatal or life-threatening suspected adverse reaction as soon as possible, but in no case later than 7 calendar days after the sponsor's initial receipt of the information. Relevant follow up information to an IND safety report will be submitted as soon as the information is available. Upon request from FDA, DMID will submit to FDA any additional data or information that the agency deems necessary, as soon as possible, but in no case later than 15 calendar days after receiving the request.

All serious events designated as "not related" to study product(s), will be reported to the FDA at least annually in a summary format.

### **9.3.3. Reporting of Pregnancy**

Pregnancies occurring in study subjects will be reported via AdvantageEDCSM on the Pregnancy Report form. No further study vaccinations will be administered to pregnant subjects, but with the subject's permission all protocol-required venous blood samples will be obtained and the subject will continue to be followed for safety for the duration of this trial. Efforts will be made to follow all pregnancies reported during the course of this trial to pregnancy outcome pending the subject's permission.

#### **9.4. Type and Duration of Follow-up of Subjects after Adverse Events**

AEs will be collected, assessed, and followed through resolution from the time of each study vaccination through approximately 21 days after the first study vaccination.

AESIs and NOCMCs will be collected, assessed, and followed through resolution from the time of the first study vaccination through approximately 3 months after the first study vaccination. SAEs will be collected, assessed, and followed from the time of the first study vaccination through resolution even if this extends beyond the trial-reporting period (through 12 months after the first vaccination).

Resolution of an AE/SAE is defined as the return to pretreatment status or stabilization of the condition with the expectation that it will remain chronic.

If the site principal investigator or appropriate sub-investigator becomes aware of an acute febrile illness and the site principal investigator or appropriate sub-investigator decides to bring the subject in for an evaluation to determine etiology, then the site principal investigator or appropriate sub-investigator, at their own discretion, can determine if specific viral testing should be done by either culture or polymerase chain reaction (PCR) to determine if the infectious agent was influenza and what strain.

Follow-up procedures, evaluations, and outcomes will be recorded on the appropriate data collection form.

#### **9.5. Halting Rules**

Further enrollment and study vaccinations will be halted for SMC review/recommendation if any of the following are reported following experimental (first) vaccination:

- Any subject experiences laryngospasm, bronchospasm, or anaphylaxis within 1 day after administration of study product that is considered related to study product.
- Two or more subjects experience the same grade 3 Adverse Event of any kind after administration of study product through day 8 that is considered related to study product
- Two or more subjects experience generalized urticaria (defined as occurring at more than two body parts) within 3 days after administration of study product that is considered related to study product.

- Any subject experiences a study vaccine-related SAE from the time of the first study vaccination through the subject's last study visit.

Grading scales for solicited upper respiratory and systemic (subjective and quantitative) reactions are included in [Section 9.2.2](#).

If any of the halting rules are met following any subject receipt of the first study vaccination, then this trial will not continue with the remaining enrollments or study vaccinations without a review by and recommendation from the SMC to proceed.

DMID retains the authority to suspend additional enrollment and study interventions/ administration of study product during the entire trial, as applicable.

## **9.6. Safety Oversight**

### **9.6.1 Independent Safety Monitor (ISM)**

The ISM is a physician with relevant expertise whose primary responsibility is to provide to DMID an independent safety assessment in a timely fashion. The ISM will review SAEs in real time and other AEs as needed and provide a written report to DMID. Participation is for the duration of the DMID study. The ISM must meet the requirements of the NIAID conflict of interest policy.

The ISM:

- Is in close proximity to the study site and has the authority and ability to readily access study participant records in real time.
- May be a member of the participating institution's staff but preferably be from a different organizational group within the institution.
- Should not be in a direct supervisory relationship with the investigator.
- Should have no direct involvement in the conduct of the study.

The ISM will:

- Sign a Conflict of Interest (COI) certification at the time they are asked to participate and provide updates to this information as needed.

- Receive reports of Serious Adverse Events (SAEs) from the site investigator and will be notified by email when DMID is notified of the SAE.
- Evaluate the SAE and report their clinical assessment to DMID, through DMID-CROMS SOCS in a timely manner using the report form and email the report to DMID-CROMS SOCS.
- Communicate with the investigator at the participating site as needed.
- Review additional safety related events at the request of DMID.
- Provide additional information to DMID and/or the DSMB by teleconference as requested.

### **9.6.2 Safety Monitoring Committee (SMC)**

This study will utilize an SMC, which is an independent group of experts that advises DMID. The primary responsibility of the SMC is to monitor subject safety. The SMC is external to DMID and comprises at least 3 voting members. The SMC will consist of members with appropriate phase 1 study expertise to contribute to the interpretation of the data from this trial. Its activities will be delineated in a SMC charter that will describe the membership, responsibilities, and the scope and frequency of data reviews. The SMC will operate on a conflict-free basis independently of the study team. The DMID or the SMC may convene ad hoc meetings of the SMC according to protocol criteria or if there are concerns that arise during the study.

The SMC will review the safety data at the following milestones:

- Organizational meeting (prior to start of the study)
- Data Review Meetings (DRM) will be held during the study. The SMC will review and evaluate accumulated trial data for subject safety, trial conduct, and trial progress at the below time points. Unless a halting rule has been met or there is a safety concern, screening, enrollment, and vaccination will continue while the data is being prepared and reviewed by the SMC for these DRMs.
  - For Dose 1 – all available safety data through Day 8 after all subjects have received 1st vaccination.

- An ad hoc SMC meeting will be convened when a halting rule is met, or at the request of the investigator and/or DMID if there are safety concerns during the course of the study.
- Early analysis review: After clinical database lock on day 57 to review the cumulative unblinded safety data for this trial. The data will be provided in a standard summary format.
- Final Data Review Meeting: May be held 6 to 8 months after final clinical database lock to review the cumulative unblinded safety and immunogenicity data for this trial. If a final review meeting is held, the data will be provided in a standard summary format. The SMC may be asked to provide recommendations in response to questions posed by DMID.

All reviews by the SMC will be performed using unblinded data. Study drug administration data, including dose interruptions, modifications, and the associated reason(s), will be reported to the SMC.

The DMID Medical Monitor is empowered to stop study enrollment and vaccine administration if adverse events that meet the halting criteria are reported or if any serious safety concerns arise. The DMID Medical Monitor and the ISM will be responsible for reviewing SAEs in real time. The SMC will review SAEs on a regular basis and ad hoc during the study.

## **10. CLINICAL MONITORING**

### **10.1 Site Monitoring Plan**

Site monitoring is conducted to ensure that the human subjects protections, study and laboratory procedures, study intervention administration, and data collection processes are of high quality and meet sponsor, ICH/GCP guidelines and applicable regulations, and that this trial is conducted in accordance with the protocol, protocol-specific MOP and applicable sponsor standard operating procedures. DMID, the sponsoring agency, or its designee will conduct site-monitoring visits as detailed in the clinical monitoring plan.

Site visits will be made at standard intervals as defined by DMID and may be made more frequently as directed by DMID. Monitoring visits will include, but are not limited to, review of regulatory files, accountability records, eCRFs, informed consent forms, medical and laboratory reports, and protocol and GCP compliance. Site monitors will have access to the participating site, study personnel, and all study documentation according to the DMID-approved site monitoring plan. Study monitors will meet with site principal investigators to discuss any problems and actions to be taken, and will document site visit findings and discussions.

## 11. STATISTICAL CONSIDERATIONS

### 11.1 Study Hypothesis

This Phase I study is exploratory, rather than confirmatory and not designed to test a formal null hypothesis. Rather, it is intended to obtain preliminary data in a pediatric population to estimate the immune response induced by this vaccine and to uncover any safety issues that occur at a sufficiently high rate that they might be observed in a study of this size.

### 11.2. Sample Size Considerations

This study is planned to enroll approximately 25 subjects in each treatment arm (Table 1). The sample size for this study was selected to obtain preliminary estimates in a pediatric population. While this study is not designed to test any specific null hypothesis, the following tables illustrate the precision and power available for select estimates and comparisons of interest.

Table 3 indicates the probability of observing one or more safety events, such as solicited local or systemic reactogenicity events or an unsolicited AE of a particular type, for a single treatment arm (N=25), and for all enrolled subjects (N=50).

**Table 3: Power (%) to Detect Safety Events:**

Event Frequency	Single Treatment Arm N=25	All Enrolled Subjects N=50
10% Very Common	93	>99
1% Common	22	40
0.1% Uncommon	3	5
0.01% Rare	<1	<1

Table 4 illustrates the minimum detectable differences in the proportion of subjects responding (e.g., attaining seroconversion or a titer  $\geq 1:40$ ) between two treatment arms for a range of possible response rates in the comparator arm, using a Chi-Square Test and  $\alpha = 0.05$ . In a Previous DMID trial (12-0016) in this population approximately 8% of subjects did not have available immunogenicity data at Day 42. Table 4 is presented for the planned enrollment (N = 25 per group) and accounting for 10% drop out (N = 22 per group).

**Table 4: Minimum Detectable Difference in Proportion Responders with 80% Power**

Assumed Proportion of Responders in Comparator Arm	N = 25	N = 22
0.20	0.36	0.40
0.40	0.36	0.40
0.60	0.31	0.33
0.80	0.20	0.20

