**Description of Study Design:** This is a Phase I randomized, double-blind, comparison trial in 50 children and adolescents, 9 to 17 years old, inclusive, who are in good health and meet all eligibility criteria. This clinical trial is designed to assess the safety and immunogenicity of a monovalent H3N2 M2SR vaccine (manufactured by FluGen) in an older pediatric population. The monovalent influenza H3N2 M2SR virus vaccine was derived from influenza strain A/Brisbane/10/2007-like H3N2 (H3N2 M2SR).

Subjects will be enrolled in one of two groups in a 1:1 ratio as indicated in Table 1. Subjects will be randomly assigned to either receive one dose of Saline intranasally or one dose of M2SR intranasally followed by one dose of licensed QIV 3 months later.

Reactogenicity will be measured for the first vaccine (first vaccination) by the occurrence of solicited reactions from the time of study vaccination through Day 8 after vaccination. Unsolicited non-serious AEs will be collected from the time of the first study

vaccination through approximately 21 days after the first study vaccination. SAEs will be collected from the time of the first study vaccination throughout the entire study. AESIs (wheezing, and otitis media) and NOCMC will be documented and reported from the time of first study vaccination through approximately 3 months after first study vaccination.

[figure not shown]
Immunogenicity testing will include performing HAI, HA/NA ELISA, neutralization, nasal secretory IgA (sIgA), IFN- $\gamma$  ELISPOT and CFSE dilution/ICS assays. Serum for HAI, HA/NA ELISA and neutralization assays will be obtained on Day 01 (pre-vaccination), Days 08, 22, and 57 after the first vaccination, immediately prior to the 2nd study vaccination (Day 92), and on Day 22 after the 2nd vaccination. Nasal swabs for sIgA will be collected on Day 01 (pre-vaccination), Days 08, 22, and 57 after the first vaccination, immediately prior to the 2nd vaccination (Day 92), and on Day 22 after the 2nd vaccination. PBMC for T cell functional assays will be harvested on Day 01 (pre-vaccination), Days 08, 22, and 57 after the first vaccination, immediately prior to 2nd vaccination (Day 92), and on Day 22 after the 2nd vaccination.

**Estimated Time to Complete Enrollment:** Approximately 3 months

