5. SAMPLE SIZE CONSIDERATIONS

This study is planned to enroll approximately 25 subjects in each treatment arm (Table 1). The sample size for this study was selected to obtain preliminary estimates in a pediatric population. While this study is not designed to test any specific null hypothesis, the following tables illustrate the precision and power available for select estimates and comparisons of interest.

Table 3 indicates the probability of observing one or more safety events, such as solicited local or systemic reactogenicity events or an unsolicited AE of a particular type, for a single treatment arm (N=25), and for all enrolled subjects (N=50).

Table 4 illustrates the minimum detectable differences in the proportion of subjects responding (e.g., attaining seroconversion or a titer $\geq 1:40$) between two treatment arms for a range of possible response rates in the comparator arm, using a Chi-Square Test and $\alpha = 0.05$. In a Previous DMID trial (12-0016) in this population approximately 8% of subjects did not have available immunogenicity data at Day 42. Table 4 is presented for the planned enrollment (N = 25 per group) and accounting for 10% drop out (N = 22 per group).

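### Table 4 credits the design with 80% power for a 0.20 difference at a comparator rate of 0.80, but that power cannot be reached in that row at either sample size

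*Protocol*

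**What the plan says.** Protocol Section 11.2 and SAP Section 5 present Table 4 in the same terms. It is titled "Minimum Detectable Difference in Proportion Responders with 80% Power", and the SAP introduces it thus: "Table 4 illustrates the minimum detectable differences in the proportion of subjects responding". The differences are given "for a range of possible response rates in the comparator arm, using a Chi-Square Test and" an alpha of 0.05; neither document says whether the test is one- or two-sided or how power was computed. Two sample sizes are shown: full enrollment of 25 per arm, and a second column "accounting for 10% drop out (N = 22 per group").

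The printed values (N=25 / N=22) are:

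| Comparator rate | N=25 | N=22 |
|---|---|---|
| 0.20 | 0.36 | 0.40 |
| 0.40 | 0.36 | 0.40 |
| 0.60 | 0.31 | 0.33 |
| 0.80 | 0.20 | 0.20 |

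No footnote qualifies the 0.80 row. Both documents also say that the study tests no specific null hypothesis and that the tables are there to illustrate precision and power.

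**The concern.** The 0.80 row equals 1 - 0.80, the ceiling on any increase, and it is the same for both sample sizes. In every other row the loss of three subjects per arm raises the value by 0.02 to 0.04. That pattern fits a bound entered where the calculation had no solution better than it fits a solved difference.

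At stake is the accuracy of a stated capability. A reader planning a later trial from this table would take it that an increase from 80% to 100% responders is detectable with 80% power, even after dropout.

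**Working it through.** **Inputs.** Power 80%, alpha 0.05 and chi-square test: Table 4 and its introduction. N per arm: 25, and 22 (25 x 0.9 = 22.5, rounded down). Allocation 1:1: Protocol Summary. Assumptions: two-sided, no continuity correction. I read the differences as increases over the comparator, because a fall of 0.36 from 0.20 is impossible.

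**Test statistic.** With n per arm, observed difference d and pooled proportion m, chi-square = d^2 / [m(1 - m)(2/n)]. It rejects at 3.841 or more.

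**Reproducing the plan's figures.** Enumerating all 2x2 tables and solving for 80% power gives the following. Power at the printed value is shown for the exact chi-square and for the pooled normal approximation.

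| Comparator | N | Exact solution | Printed | Exact power | Pooled power |
|---|---|---|---|---|---|
| 0.20 | 25 | 0.365 | 0.36 | 78.9% | 76.2% |
| 0.40 | 25 | 0.368 | 0.36 | 78.2% | 74.7% |
| 0.60 | 25 | 0.317 | 0.31 | 77.2% | 73.6% |
| 0.80 | 25 | none | 0.20 | 76.6% | 66.3% |
| 0.20 | 22 | 0.404 | 0.40 | 79.1% | 79.4% |
| 0.40 | 22 | 0.404 | 0.40 | 79.1% | 79.4% |
| 0.60 | 22 | 0.334 | 0.33 | 78.6% | 75.0% |
| 0.80 | 22 | none | 0.20 | 66.8% | 60.5% |

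Cut to two decimals, the exact solutions give all six cells outside the 0.80 row. The same calculation has no solution in the 0.80 row.

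**The 0.80 row by hand, N=25.** At 100% response the other arm is 25/25 with certainty.
- Comparator 21/25: d = 0.16, m = 46/50 = 0.92, chi-square = 0.0256 / 0.005888 = 4.35, which rejects.
- Comparator 22/25: d = 0.12, m = 0.94, chi-square = 0.0144 / 0.004512 = 3.19, which does not.
- Power = P(X <= 21) for X ~ Binomial(25, 0.80) = 76.6%.

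**N=22.** Comparator 18/22 gives 4.40 and rejects; 19/22 gives 3.22 and does not. Power = P(X <= 18) for X ~ Binomial(22, 0.80) = 66.8%.

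**Pooled normal approximation.** Power = Phi{[0.20 - 1.96 sqrt(2 x 0.9 x 0.1 / n)] / sqrt(0.8 x 0.2 / n)}.
- N=25: (0.20 - 1.96 x 0.08485) / 0.0800 = 0.421, so 66.3%.
- N=22: (0.20 - 1.96 x 0.09045) / 0.0853 = 0.266, so 60.5%.

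**How far off.** Comparing 0.80 with 1.00 at 80% power needs 27 per arm by exact enumeration (81.8%; 26 gives 79.3%) or 35 by the pooled formula. With 100% response in the other arm, exact power reaches 80% only if the comparator rate is at most about 0.790 (N=25) or 0.763 (N=22).

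**Rounding the other cells up.** Exact power becomes 81.1%, 80.5% and 81.0% at 0.37, 0.37 and 0.32 (N=25), and 81.1%, 81.4% and 82.4% at 0.41, 0.41 and 0.34 (N=22).

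**The case against.** **Another method may lie behind the table.** The arcsine approximation has solutions in the 0.80 row (0.196 and 0.199, both rounding to 0.20), and at N=22 it matches the whole printed column. It fails at N=25: the half-step is (1.960 + 0.842) / sqrt(50) = 0.396, so a comparator of 0.20 gives sin^2(0.464 + 0.396) - 0.20 = 0.374, against 0.36 printed. At an other-arm rate of 0.996, which is the N=25 arcsine solution, the chi-square test has exact power of only 72.8% (N=25) and 63.3% (N=22). One-sided exact testing gives 90.2% and 84.6% in the 0.80 row, but puts the other cells at 85-88%, so it does not explain the table. An exact likelihood-ratio calculation also exceeds 80% there, but it is not the usual Pearson test and does not match the N=25 cells with consistent rounding. None of these rescues the row. What stands is that the documents do not name the method, so the size of the shortfall depends on it.

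**The remaining cells are nearly right.** This stands. Four of the six equal ordinary nearest rounding of the exact solution; the exceptions are 0.40 and 0.60 at N=25, each by 0.01. Rounding a minimum detectable difference up is a convention. A reader might infer that the whole table is unsound, but a shortfall of 1 to 3 points of exact power does not support that.

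**No test depends on the table.** This also stands. A reader might infer that a null comparison after QIV would be wrongly read as no priming effect. No between-arm responder test is planned: SAP Section 8 gives HAI and neutralization responder proportions with confidence intervals by arm, and the shells for SAP Tables 20 and 26 have no difference or p-value column. Nor do the documents give an expected comparator rate that would make the 0.80 row the relevant one.

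**Table 3.** A reader might extend the criticism to its N=50 column. That column is labelled as all enrolled subjects, the single-arm figure stands beside it, and the remaining discrepancies are half-point rounding.

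**Conclusion.** The 0.80 row is wrong under its own stated test. No increase up to the maximum of 0.20 reaches 80% power at 25 or 22 per arm. The best attainable is 76.6% exact or 66.3% pooled with 25, and 66.8% or 60.5% with 22. The conclusion assumes a two-sided, uncorrected chi-square test.

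The consequence is a misstated capability in an illustrative table. The documents do not support reading it as a flaw in the sample size, which was chosen for preliminary estimates, or in any planned analysis.

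**What to change.** In Table 4 of both the Protocol and the SAP:

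- Replace the two 0.80-row cells with: 80% power not attainable; maximum power about 77% (N=25) and 67% (N=22) by exact chi-square, even with 100% response.
- State the calculation method and the sidedness, for example exact enumeration of the uncorrected chi-square test, two-sided.
- As a minor accompanying change, round the other cells up (N=25/N=22): 0.37/0.41 at a comparator of 0.20, 0.37/0.41 at 0.40, and 0.32/0.34 at 0.60. These reach 80% under the exact calculation; if the sponsor names another method, the cells should be recomputed by it.

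The cost is one table edit and one sentence in each document, with slightly less favourable printed figures. Sample size, conduct and analyses are unaffected.
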